9.1.6 Changes in Clinical Laboratory Test Values

It is the investigator's (or designee's) responsibility to review the results of all laboratory tests as they become available. This review will be documented by the investigator's dated signature on the laboratory report. For each abnormal laboratory test result, the investigator needs to ascertain if this is an abnormal (ie, clinically significant) change from baseline for that individual participant. This determination, however, does not necessarily need to be made the first time an abnormal value is observed. The investigator may repeat the laboratory test or request additional tests to verify the results of the original laboratory tests. If this laboratory value is considered medically relevant by the investigator (participant is symptomatic, requiring corrective treatment or further evaluation), or if the laboratory value leads to discontinuation, and/or fulfills a seriousness criterion, this is considered an AE.

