8.3.10 Number of Cigarettes Daily

The summary statistics for changes from baseline in the average number of cigarettes smoked per day will be provided.

9 Safety Analyses

Safety assessments including AEs, vital signs, ECGs, clinical laboratory tests (serum chemistry, hematology, and urinalysis) will be summarized for the Safety Analysis Set.

In summarizing the incidence of clinically relevant abnormalities in clinical laboratory results, vital sign measurements and ECG measurements, a subject must have had an evaluation that meets the specified criteria. For clinical laboratory results and ECG measurements, incidence rate will be calculated as the number of subjects having at least one abnormality divided by the number of subjects in the Safety Analysis Set. For vital sign measurements, incidence rate will be calculated as the number of subjects having at least one abnormality divided by the number of subjects in the Safety Analysis Set.

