9.3 Clinical Laboratory Data

Hematology and serum chemistry will be collected at screening visit, Week 3 visit and Week 7 visit. Urinalysis will be collected at screening visit and Week 7 visit. The baseline for laboratory analyses is defined as the last evaluable assessment prior to first IMP. The summary statistics for changes from baseline in the clinical laboratory measurements will be provided. The incidences and percentage of potentially clinically relevant laboratory tests abnormalities will be summarized. The potentially clinically relevant laboratory test abnormalities will be listed by subject and by test. The criteria for Identifying Laboratory Values of Potential Clinical Significance are provided in [Appendix 2](#). Potential Hy's law cases will be displayed in a listing. The laboratory results for serum chemistry, hematology, and urinalyses will be listed.

If laboratory tests assessments are repeated for the same visit window, the last repeated values will be used for summary tables. This is accomplished by sorting patient data by visit date and visit time (if applicable) within same visit window. If the lab data are recorded as ranges (i.e., including < or > limit of quantification), these data are not included in the calculations for changes from baseline but included in the calculations for incidences.

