9.4 Vital Sign Data

Vital signs include systolic and diastolic blood pressure, pulse rate, temperature and respiratory rate. The potential clinically relevant vital sign abnormalities will be listed by subject. Criteria for the potentially clinically relevant vital sign abnormalities are provided in [Appendix 1](#). Incidences of clinically relevant vital signs abnormalities based

Protocol 405-201-00055 Statistical Analysis Plan

on the observation from the scheduled visits and unscheduled post-baseline visits will be tabulated. In addition, vital sign parameters and changes from baseline at trial visits and last visit will be summarized.

If vital sign assessments are repeated for the same visit window, the last repeat values will be used for production of summary tables. This is accomplished by sorting patient data by visit date and visit time (if applicable) within the same visit window.

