9.6 Electrocardiogram Data

A standard 12-lead ECG will be recorded after the participant has rested for at least 5 minutes in a supine position. The RR, PR interval, QRS duration, QT intervals, and QTc are recorded. The corrected QT intervals for QTcF are defined as follows:

QTcF is the length of the QT interval corrected for heart rate by Fredericia's formula:
$$QTcF = QT / (RR)^{1/3}$$

The potentially clinically relevant ECG abnormalities will be listed by subject. Criteria for potentially clinically relevant ECG abnormalities are provided in [Appendix 3](#). The incidences of abnormal ECGs of potentially clinical relevance based on the observation at the scheduled and the unscheduled post-baseline visits will be tabulated. Descriptive statistics of change from baseline in ECG intervals of PR, QRS, RR, QT, and QTcF at scheduled visits and last visit will be presented.

If ECG assessments are repeated for the same visit window, the last repeat values will be used for production of mean change from baseline. This is accomplished by sorting patient data by visit date and visit time (if applicable) within the same visit window.

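### SAP 9.3 applies the last-repeat rule to laboratory summary tables without exempting the incidence table CT-10.1, which conflicts with the at-least-one-abnormality count in SAP 9

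*SAP*

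**What the plan says.** SAP 9.3 (laboratory data), for tests repeated in the same visit window: "the last repeated values will be used for summary tables". The section also plans a summary of the incidence of potentially clinically relevant abnormalities, which is CT-10.1 in SAP 17. The repeat rule does not separate that table from the change-from-baseline tables.

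SAP 9 (opening text on safety analyses) sets the incidence rule. To be counted, "a subject must have had an evaluation that meets the specified criteria". It continues: "For clinical laboratory results and ECG measurements, incidence rate will be calculated as the number of subjects having at least one abnormality", divided by the Safety Analysis Set.

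SAP 9.6 (ECG) words its repeat rule more narrowly: "the last repeat values will be used for production of mean change from baseline". It takes ECG incidence from scheduled and unscheduled post-baseline visits.

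SAP 9.4 (vital signs) has the broad wording, "the last repeat values will be used for production of summary tables", but also takes incidence from scheduled and unscheduled post-baseline visits.

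Protocol 9.1.6, on abnormal laboratory results: "The investigator may repeat the laboratory test or request additional tests to verify the results of the original laboratory tests".

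**The concern.** Two instructions bear on CT-10.1 and the SAP does not say which governs. One keeps only the last value in a window. The other counts a participant with any abnormality.

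The choice matters because repeats are not taken at random. The protocol foresees them as a check on abnormal results, so the value that the last-repeat rule discards will tend to be the abnormal one.

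There is little redundancy in the schedule. Chemistry and hematology have two scheduled on-treatment samples (V4 and V6; protocol 6.5.1 and 6.5.2), and urinalysis has one (V6; protocol 6.5.4). A single superseded value could be a participant's only abnormal result. At stake is whether a reported safety rate depends on how a programmer reads one sentence.

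**Working it through.** The plan states no figure on this point, so there is nothing to reproduce. The check compares the texts and then sizes one affected case.

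**1. The three safety domains side by side**

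| Domain | Last-repeat rule applies to | Incidence stated to use unscheduled visits |
|---|---|---|
| Laboratory (9.3) | summary tables, no limit | no |
| Vital signs (9.4) | summary tables, no limit | yes |
| ECG (9.6) | mean change from baseline only | yes |

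Only the laboratory section lacks both safeguards.

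**2. Two ways to program CT-10.1**

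- Reading A: keep the last value per window, then count a participant if any kept value meets the criterion. This applies 9.3 literally and can still be said to follow SAP 9, which does not define the eligible records.
- Reading B: count a participant if any post-first-dose value meets the criterion. This is the plain sense of SAP 9.

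The values used in A are a subset of those used in B. For any criterion, the numerator under A therefore cannot exceed the numerator under B. Any difference runs in one direction.

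**3. One hypothetical participant**

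SAP Appendix 2 sets the ALT criterion at 3 × ULN or more. Suppose ALT is 3.5 × ULN at V4, 1.5 × ULN on a repeat in the same window, and normal at V6.

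- Reading A: not counted, contribution 0/50.
- Reading B: counted, contribution 1/50 = 2.0%.

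**4. Size**

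Inputs: N = 50 (SAP 3.3, used as the approximate Safety Analysis Set); k = participants with at least one abnormal value; m = those among them whose only abnormal value is superseded in its own window.

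Reading B = k/50. Reading A = (k − m)/50. Difference = m/50, or 2.0 percentage points per case.

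Illustration with k = 5 (assumed):

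| m | Reading B | Reading A |
|---|---|---|
| 0 | 10.0% | 10.0% |
| 1 | 10.0% | 8.0% |
| 3 | 10.0% | 4.0% |
| 5 | 10.0% | 0.0% |

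Neither document gives a repeat rate or a normalisation rate, so m is unknown.

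**5. What the same visit window means**

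The only window table in the SAP, Table 5.4-1, is titled for efficacy. If it were used for laboratory data, a V4 sample on Day 21 would map to Week 3 and a repeat on Day 24 to Week 4; both values would survive. Taking V6 as Day 49 ± 3 gives Days 46 to 52, and Days 50 to 52 lie beyond the table, which ends at Day 49. The laboratory window is thus undefined, and whether a given repeat supersedes the first value is a further matter of interpretation.

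**The case against.** The strongest reply is that SAP 9 already settles the matter. It requires only an evaluation that meets the criterion and counts participants with at least one abnormality, so a plain reading keeps the participant in the example. Other text supports a narrow sense of summary tables. SAP 5.4 uses the phrase for tables by trial week. SAP 9.3 itself, when dealing with values recorded as ranges, treats change from baseline and incidence separately. The heading over the table list in SAP 17 is weak evidence the other way, because that list also contains listings and criteria tables.

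This defeats one stronger reading that a reader might take: that abnormal values will drop out of CT-10.1. The documents do not establish that. They leave the matter open, because SAP 9 does not name the eligible records and 9.3 places no limit on its rule.

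A reader might also infer that vital-sign incidence (CT-11.1) is equally exposed. It is largely protected by the unscheduled-visit sentence in 9.4; what remains is at most a repeat within a single visit.

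A reader might go on to estimate the share of abnormal cases lost by multiplying assumed repeat and normalisation rates. No such rates appear in either document, and protocol 9.1.6 permits a repeat without requiring one.

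Finally, laboratory signals would not be hidden. Abnormal values are listed by subject and by test (CT-10.3.1, CT-10.3.2), potential Hy's law cases are listed (CT-10.6), and 9.3 lists all laboratory results. Under protocol 9.1.6, values that the investigator judges medically relevant, that lead to discontinuation, or that meet a seriousness criterion become adverse events. These safeguards limit the harm, but none of them corrects a reported incidence rate.

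**Conclusion.** The concern holds as an unresolved conflict. Read literally, SAP 9.3 reaches CT-10.1 and can remove a participant whom SAP 9, read plainly, would count. The loss needs three conditions: the repeat falls in the same (undefined) laboratory window, it no longer meets the criterion, and no retained value in any window does. Each such case lowers the reported incidence by 2 percentage points, assuming 50 dosed participants. The number of cases cannot be derived from the documents.

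The effect is confined to a descriptive safety table. The primary endpoint and its interval are untouched. The point still deserves correction before programming, because any error can only lower the rate and the SAP already has the right wording for ECGs.

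**What to change.** In SAP 9.3, limit the last-repeat rule to by-visit descriptive tables and change-from-baseline tables, in line with the restriction already in 9.6. Add a statement that CT-10.1 uses every post-first-dose value, whether scheduled, unscheduled or repeated, and that a participant is counted if any value meets the criterion. The same wording change in 9.4 would be for consistency only.

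This takes about two sentences and no new data. The downside is a slightly higher reported abnormality rate, including some values that a repeat did not confirm; the existing listings let a reader identify those.

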9.4 Vital Sign Data

Vital signs include systolic and diastolic blood pressure, pulse rate, temperature and respiratory rate. The potential clinically relevant vital sign abnormalities will be listed by subject. Criteria for the potentially clinically relevant vital sign abnormalities are provided in [Appendix 1](#). Incidences of clinically relevant vital signs abnormalities based

Protocol 405-201-00055 Statistical Analysis Plan

on the observation from the scheduled visits and unscheduled post-baseline visits will be tabulated. In addition, vital sign parameters and changes from baseline at trial visits and last visit will be summarized.

If vital sign assessments are repeated for the same visit window, the last repeat values will be used for production of summary tables. This is accomplished by sorting patient data by visit date and visit time (if applicable) within the same visit window.

9.5 Physical Examination Data

A complete physical examination include review of general appearance, hair and skin, head, eyes, ears, nose and throat, neck, chest, abdomen, dentition, cardiovascular, musculoskeletal and neurological systems will be performed.

A listing of physical examination outcome will be provided.

9.6 Electrocardiogram Data

A standard 12-lead ECG will be recorded after the participant has rested for at least 5 minutes in a supine position. The RR, PR interval, QRS duration, QT intervals, and QTc are recorded. The corrected QT intervals for QTcF are defined as follows:

QTcF is the length of the QT interval corrected for heart rate by Fredericia's formula:
$$QTcF = QT / (RR)^{1/3}$$

The potentially clinically relevant ECG abnormalities will be listed by subject. Criteria for potentially clinically relevant ECG abnormalities are provided in [Appendix 3](#). The incidences of abnormal ECGs of potentially clinical relevance based on the observation at the scheduled and the unscheduled post-baseline visits will be tabulated. Descriptive statistics of change from baseline in ECG intervals of PR, QRS, RR, QT, and QTcF at scheduled visits and last visit will be presented.

If ECG assessments are repeated for the same visit window, the last repeat values will be used for production of mean change from baseline. This is accomplished by sorting patient data by visit date and visit time (if applicable) within the same visit window.

9.7 Suicidality

Suicidality will be assessed based on Columbia-suicide severity rating scale (C-SSRS) data. Data for the "Baseline" Version of the C-SSRS and **CCI**

[REDACTED]

[REDACTED]

[figure not shown]
[REDACTED]

Protocol 405-201-00055 Statistical Analysis Plan

The “Baseline” version of the C-SSRS will be completed at screening **CCI**

CCI

10 Pharmacokinetic Analyses

Blood samples will be taken to determine concentrations of centanafadine and metabolites to assess compliance with dosing.

11 Pharmacodynamic Analyses

No pharmacogenomic analyses is planned.

12 Pharmacogenomic Analyses

No pharmacogenomic analyses is planned.

13 Interim Analysis

No interim analyses are planned.

Protocol 405-201-00055 Statistical Analysis Plan

14 Changes in the Planned Analyses

None.

Protocol 405-201-00055 Statistical Analysis Plan

15 References

- ¹ Reus VI, Obach RS, Coe JW, et al. Varenicline: new treatment with efficacy in smoking cessation. *Drugs Today Barc Spain* 1998. 2007;43(2):65-75. doi:10.1358/dot.2007.43.2.1069956
- ² Lee YY, Khoo S, Morris T, et al. A mixed-method study of the efficacy of physical activity consultation as an adjunct to standard smoking cessation treatment among male smokers in Malaysia. *SpringerPlus*. 2016;5(1):2012. doi:10.1186/s40064-016-3675-2
- ³ Teo, E. W., Lee, Y. Y., Khoo, S., Morris, T. Translation and validation of the MALAY version OF Shiffman-Jarvik withdrawal scale and Cessation SELF-EFFICACY Questionnaire: A review of psychometric properties. *Health and Quality of Life Outcomes*. 2015; 13(1). <https://doi.org/10.1186/s12955-015-0238-0>
- ⁴ Toll BA, O'Malley SS, McKee SA, Salovey P, Krishnan-Sarin S. Confirmatory Factor Analysis of the Minnesota Nicotine Withdrawal Scale. *Psychol Addict Behav J Soc Psychol Addict Behav*. 2007;21(2):216-225. doi:10.1037/0893-164X.21.2.216

Protocol 405-201-00055 Statistical Analysis Plan

16 Potential Clinical Relevance Criteria**Appendix 1 Criteria for Identifying Vital Signs and Weight of Potential Clinical Relevance**

Variable	Criterion Value ^a	Change Relative to Baseline ^a
Heart Rate ^b	> 100 bpm < 50 bpm	≥ 10 bpm increase ≥ 10 bpm decrease
Systolic Blood Pressure ^b	≥ 140 mmHg < 90 mmHg	≥ 20 mmHg increase ≥ 20 mmHg decrease
Diastolic Blood Pressure ^b	≥ 90 mmHg < 60 mmHg	≥ 10 mmHg increase ≥ 10 mmHg decrease
Orthostatic Hypotension	≥ 30 mmHg decrease in systolic blood pressure or a ≥ 20 mmHg in diastolic blood pressure after at least 3 minutes of standing compared to the previous supine blood pressure.	Not Applicable (baseline status not considered)
Orthostatic Tachycardia	≥ 25 bpm increase in heart rate from supine to standing	Not Applicable (baseline status not considered)
Weight	-	≥ 7% increase ≥ 7% decrease

a In order to be identified as potentially clinically relevant, an on-treatment value must meet the “Criterion Value” and also represent a change from the subject’s baseline value of at least the magnitude shown in the “Change Relative to Baseline” column.

b As defined in “Supplementary Suggestions for Preparing an Integrated Summary of Safety Information in an Original NDA Submission and for Organizing Information in Periodic Safety Updates,” FDA Division of Neuropharmacological Drug Products draft (2/27/87).

Protocol 405-201-00055 Statistical Analysis Plan

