5.2 Safety Analysis Set (SAS)

Safety Analysis Set includes all subjects who are administered at least one dose of IMP, regardless of any protocol violation.

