Appendix 2 Criteria for Identifying Laboratory Values of Potential Clinical Relevance

Laboratory Tests		Criteria
Chemistry		
AST (SGOT)		$\geq 3 \times$ upper limit of normal (ULN)
ALT (SGPT)		$\geq 3 \times$ ULN
Alkaline phosphatase		$\geq 3 \times$ ULN
BUN		≥ 30 mg/dL
Creatinine		≥ 2.0 mg/dL
Uric Acid		
Men		≥ 10.5 mg/dL
Women		≥ 8.5 mg/dL
Bilirubin (total)		≥ 2.0 mg/dL
Creatine Phosphokinase (CPK)		$> 3 \times$ ULN
Hematology		
Hematocrit		
Men		$\leq 37\%$ and decrease of ≥ 3 percentage points from Baseline
Women		$\leq 32\%$ and decrease of ≥ 3 percentage points from Baseline
Hemoglobin		
Men		≤ 11.5 g/dL
Women		≤ 9.5 g/dL
White blood count		$\leq 2,800/\text{mm}^3$ or $\geq 16,000/\text{mm}^3$
Eosinophils		$\geq 10\%$
Neutrophils		$\leq 15\%$
Absolute neutrophil count		$\leq 1,500/\text{mm}^3$
Platelet count		$\leq 75,000/\text{mm}^3$ or $\geq 700,000/\text{mm}^3$
Urinalysis		
Protein		Increase of ≥ 2 units
Glucose		Increase of ≥ 2 units
Additional Criteria		
Chloride		≤ 90 mEq/L or ≥ 118 mEq/L
Potassium		≤ 2.5 mEq/L or ≥ 6.5 mEq/L
Sodium		≤ 126 mEq/L or ≥ 156 mEq/L
Calcium		≤ 8.2 mg/dL or ≥ 12 mg/dL
Glucose		
Fasting		≥ 100 mg/dL
Non-Fasting		≥ 200 mg/dL
Total Cholesterol, Fasting		≥ 240 mg/dL
LDL Cholesterol, Fasting		≥ 160 mg/dL
HDL Cholesterol, Fasting		
Men		< 40 mg/dL
Women		< 50 mg/dL
Triglycerides, Fasting		≥ 150 mg/dL

Protocol 405-201-00055 Statistical Analysis Plan

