CT-8.8.2 Incidence of Treatment-emergent Adverse Events related to Abuse-Potential by System Organ Class and MedDRA Preferred Term and Severity (Safety Analysis Set)

CT-9.1 Listing of Deaths (Safety Analysis Set)

CT-9.2 Listing of Serious Adverse Events (Safety Analysis Set)

CT-9.3 Listing of Adverse Events Resulting in Discontinuations of IMP (Safety Analysis Set)

CT-9.4 Listing of Treatment-emergent Adverse Events of Special Interests (Safety Analysis Set)

CT-9.5 Listing of Treatment-emergent Adverse Events related to Abuse-Potential (Safety Analysis Set)

CT-10.1 Incidence of Laboratory Test Results of Potential Clinically Relevance (Safety Analysis Set)

CT-10.2.1 Laboratory Test Results for Chemistry - Mean Change from Baseline (Safety Analysis Set)

CT-10.2.2 Laboratory Test Results for Hematology - Mean Change from Baseline (Safety Analysis Set)

CT-10.2.3 Laboratory Test Results for Urinalysis - Mean Change from Baseline (Safety Analysis Set)

Protocol 405-201-00055 Statistical Analysis Plan

CT-10.2.4 Laboratory Test Results for Other Clinical Laboratory Tests - Mean Change from Baseline (Safety Analysis Set)

CT-10.2.5 Shift Tables of Clinical Laboratory Test Results - Chemistry (Safety Analysis Set)

CT-10.2.6 Shift Tables of Clinical Laboratory Test Results - Hematology (Safety Analysis Set)

CT-10.2.7 Shift Tables of Clinical Laboratory Test Results - Urinalysis (Safety Analysis Set)

CT-10.2.8 Shift Tables of Clinical Laboratory Test Results - Other Clinical Laboratory Tests (Safety Analysis Set)

CT-10.3.1 Listing of Laboratory Values of Potential Clinical Relevance by Subject (Safety Analysis Set)

CT-10.3.2 Listing of Laboratory Values of Potential Clinical Relevance by Test (Safety Analysis Set)

CT-10.5 Criteria for Laboratory Values of Potential Clinical Relevance

CT-10.6 Listing of Potential Hy's Law Cases by Subject (Safety Analysis Set)

CT-11.1 Incidence of Vital Signs of Potential Clinical Relevance (Safety Analysis Set)

CT-11.2 Vital Sign Parameters - Mean Change from Baseline (Safety Analysis Set)

CT-11.3 Listing of Vital Signs of Potential Clinical Relevance by Subject (Safety Analysis Set)

CT-11.4 Criteria for Potentially Clinically Relevant Vital Sign Abnormalities

CT-12.1 Incidence of ECG Measurements of Potential Clinical Relevance (Safety Analysis Set)

CT-12.2 ECG Parameters - Mean Change from Baseline (Safety Analysis Set)

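### The two orthostatic criteria in SAP Appendix 1 need on-treatment supine and standing pairs that the protocol does not schedule, and the protocol contradicts itself on standing readings

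*SAP*

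**What the plan says.** **SAP.** Appendix 1 has two postural rows. Orthostatic hypotension is a fall of at least 30 mmHg systolic or 20 mmHg diastolic "after at least 3 minutes of standing compared to the previous supine blood pressure". Orthostatic tachycardia is a rise of at least 25 bpm, worded as "increase in heart rate from supine to standing". The change-from-baseline column does not apply to these rows, but footnote a still restricts flags to treatment: "In order to be identified as potentially clinically relevant, an on-treatment value must meet the" criterion value. Section 9.4 tabulates the incidence from scheduled and unscheduled post-baseline visits, and section 17 lists the resulting table as CT-11.1. Section 9 says that "a subject must have had an evaluation that meets the specified criteria", and then defines the vital-sign rate as subjects with at least one "abnormality divided by the number of subjects in the Safety Analysis Set". Section 5.2 defines that set as everyone given at least one dose.

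**Protocol.** Section 6.5.8 takes vital signs sitting after five minutes' rest and adds a standing blood pressure and pulse, after two minutes on the feet, at V1 only. The V1 list in 6.6.1 agrees. The V2 to V6 lists (6.6.2 to 6.6.6) give sitting readings only. Table 6 in section 6.8 instead has one blood-pressure row covering both sitting and standing, marked at V1 through V6. It gives no standing time, and its separate heart-rate row gives no posture. The only supine procedure is the ECG (6.5.7), which Table 6 schedules at V1 and V6.

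**The concern.** Two problems meet here. First, the SAP criteria rest on a posture change, lying to standing, that the protocol's vital-sign procedure does not measure. Second, the protocol gives sites two incompatible instructions on whether standing blood pressure is taken during treatment.

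The SAP does not say what happens to a criterion without source data, so three results are possible for CT-11.1:

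- both rows print 0%, and a reader takes not measured to mean not observed;
- the rows are dropped without comment;
- a programmer substitutes the sitting reading as the reference, which changes the definition without a record.

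The topic is not remote for this drug. Protocol 7.3.1 names a heart-rate increase on rising from a seat among the common adverse effects. That is a sitting-to-standing change, so the Appendix 1 row does not target it either.

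**Working it through.** No power or error-rate calculation applies, and the plan gives no figure to reproduce. The check compares what Appendix 1 requires with what each protocol passage schedules.

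**Visits.** There are six, V1 to V6. V2 is Day -1, before the first dose, so the on-treatment visits are V3, V4, V5 and V6: four.

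| Reading | V1 to V6 | On treatment, V3 to V6 |
|---|---|---|
| Supine blood pressure | 0 of 6 | 0 of 4 |
| Supine heart rate, obtainable only from the ECG | 2 of 6 (V1, V6) | 1 of 4 (V6) |
| Standing blood pressure, by 6.5.8 and the visit lists | 1 of 6 (V1, two minutes) | 0 of 4 |
| Standing blood pressure, by Table 6 | 6 of 6 (no time given in the table) | 4 of 4 (no time given) |
| Standing pulse explicitly specified | 1 of 6 (V1, two minutes) | 0 of 4 |

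**Hypotension row.** It needs a supine blood pressure and a standing one after at least 3 minutes, on treatment. The supine half is missing at every visit, so the count is 0 of 4 whichever protocol passage governs. The one standing time that the protocol states, two minutes, also falls short of the 3 minutes in the criterion.

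**Tachycardia row.** It needs a supine and a standing heart rate, on treatment, and sets no standing time. The supine half exists only at V6, from the ECG. No passage schedules a standing pulse at V6, and the V6 list places pulse among the sitting measurements. The count is again 0 of 4.

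**Effect on the printed rate.** Suppose all 50 planned subjects are dosed and only scheduled visits contribute:

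- Rate by SAP section 9: events ÷ Safety Analysis Set = 0 ÷ 50 = 0%.
- Rate among subjects who could be assessed: 0 ÷ 0, which is undefined.

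The section 9 sentence requiring an evaluation that meets the criteria limits who counts as an event. It does not alter the denominator stated after it.

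**Unscheduled visits.** SAP 9.4 admits them, but neither document says that readings there are taken supine and then standing.

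**The case against.** The strongest case concerns weight. This is a single-arm, open-label, descriptive study of 50 subjects. No test, endpoint or stated decision rule uses these two rows. The ordinary heart-rate and blood-pressure criteria can still be evaluated from sitting readings, and symptomatic events reach the adverse-event tables. That stands, and it limits the consequence.

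Next, the misleading 0% is inferred. There is no table shell, and section 17 is only a proposed list. Appendix 2 includes six tests absent from protocol Table 1 (uric acid, creatine phosphokinase, total cholesterol, LDL, HDL and triglycerides), which suggests a standard list whose unused rows may simply be left out. That is plausible, but the SAP does not say so. The rule it does state gives 0%, and an undocumented omission or substitution is what a SAP is meant to prevent.

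Third, the zero for tachycardia is less secure than the zero for hypotension. A supine rate can be derived from the V6 ECG, and Table 6's heart-rate row is silent on posture, so a standing pulse at V6 would make a pair conceivable at 1 of 4 visits. But no passage schedules that pulse, the V6 list says sitting, and 6.6.6 leaves the order of assessments to the investigator, so the ECG rate need not precede standing. The zero holds for what is scheduled.

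Last, a separate denominator for two rows departs from the convention in section 9. If the rows are removed, the point falls away. If they are kept, the number of evaluable subjects is needed to read them.

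**Conclusion.** The concern holds in both parts. As written, neither orthostatic criterion can be evaluated from the scheduled visits: 0 of 4 on-treatment visits gives a complete pair for either row, and so 0 of the planned 50 subjects is evaluable from scheduled data. Separately, standing blood pressure during treatment is scheduled at 0 of 4 visits by protocol 6.5.8 and the visit lists, and at 4 of 4 by Table 6. A site cannot follow both.

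The counts come from the documents alone and assume no event rates. They take the protocol's silence on a standing pulse after V1 as meaning that none is scheduled. The 0 of 50 assumes that all planned subjects are dosed and that no unscheduled supine and standing pair is recorded.

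This should be corrected, but the reach is small: two rows in CT-11.1 and the corresponding entries in listing CT-11.3. The primary and secondary endpoints do not depend on it.

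**What to change.** 1. Reconcile protocol 6.5.8, the V2 to V6 visit lists, Table 6 and SAP Appendix 1 on posture, standing time, visits, and whether standing pulse is taken. Which version is right, and any threshold or timing, is for the sponsor's clinical team.
2. Align the two Appendix 1 rows with the readings that are then collected, or remove a row that has no source data and say so in the SAP.
3. Add one sentence to SAP section 9: for any postural row that is kept, CT-11.1 shows the number of subjects with a paired on-treatment postural reading and uses it as the denominator. Print 'not evaluable' if there are none.

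The text cost is two appendix rows, one sentence in the SAP and a protocol clarification. The measurement cost depends on which passage governs. If Table 6 governs, standing blood pressure is already scheduled, and a brief reading per visit is added only if the sponsor decides that standing pulse is to be taken. If 6.5.8 and the visit lists govern, no on-treatment standing reading exists. Both rows then come out or read 'not evaluable', unless the sponsor chooses to add readings.
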